### 3.4.5 Dose selection

The starting dose in the dose escalation phase of the study will be 5 mg b.i.d. The dose selection was based on the findings of the [INCB 18424-251] study that has established thrombocytopenia as the DLT of INC424 in MF patients, with a MTD of both 25 mg b.i.d. and 100 mg qd. The incidence of grade  $\geq 3$  thrombocytopenia in this phase I/II trial was 20% at 10 mg b.i.d., 2.9% at 15 mg b.i.d. and 36% at 25 mg b.i.d. Grade 4 thrombocytopenia events occurred with an incidence of 0%, 0% and 11% for patients who initiated dosing at 10 mg b.i.d., 15 mg b.i.d. or 25 mg b.i.d., respectively. Data from that study showed that patients who entered the study with baseline PLT counts  $100-150 \times 10^9/L$  developed grade  $\geq 2$  thrombocytopenia more frequently (75% vs. 37%, respectively, for the most commonly used doses that will be relevant to this trial, 10 mg and 15 mg b.i.d.) compared with patients with baseline PLT counts  $> 150 \times 10^9/L$ . Thrombocytopenia occurred rapidly (Figure 1-1 and Figure 1-2) and resolved with brief drug interruptions and restarts at (usually) lower doses. Analysis of patients who enrolled in the [INCB 18424-251] study with platelet counts  $< 150 \times 10^9/L$  and had extended (many weeks) periods of grade 1 or 2 platelet decline was carried out, in order to identify the dose(s) associated with stable platelet counts in the range of  $50 \times 10^9/L$  to  $100 \times 10^9/L$ . Fourteen patients were identified that fit these criteria; 9 of the patients maintained platelet counts between  $50 \times 10^9/L$  and  $100 \times 10^9/L$  while receiving 5 mg b.i.d., 2 patients maintained platelets in this range taking 10 mg b.i.d., one patient was receiving 5 mg q.AM / 10 mg q.PM, one was receiving 5 mg qd and one was receiving 10 mg qd. Importantly, splenomegaly and/or symptom improvements were maintained in 11 of the 14 patients at a level similar to that observed with their initial, higher dose regimen. [REDACTED]

During the dose escalation phase, the following dose levels are planned to be tested with regards to safety, particularly:

- 5 mg q.AM / 5 mg q.PM
- 5 mg q.AM / 10 mg q.PM
- 10 mg q.AM / 10 mg q.PM
- 10 mg q.AM / 15 mg q.PM, and
- 15 mg q.AM / 15 mg q.PM.

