#### **5.1.4 Treatment interruption and treatment discontinuation**

Patients may continue treatment with INC424 for the duration of the study or until they experience unacceptable toxicity that precludes any further treatment, disease progression, and/or at the discretion of the Investigator. Patients will be discontinued from the study if they withdraw consent, or if the treating physician judges that further therapy with INC424 is no longer in the patient's best interest.

Criteria for interruption and re-initiation of INC424 treatment are summarized in the [Table 5-4](#). A patient must discontinue treatment with INC424 if, after treatment is resumed at a lower dose, the same toxicity recurs with the same or worse severity. If a patient requires a dose delay of > 28 days, then the patient must be discontinued from the study. Patients who discontinue from the study for a treatment-related adverse event or a treatment-related abnormal laboratory value must be followed as described in [Section 6.1.4](#).

Grading of toxicity will be according to CTCAE Version 4.03.

Doses may be restarted and subsequently increased, according to the [Table 5-6](#), provided that platelet counts recover to  $\geq 35 \times 10^9/L$  and ANC counts recover to  $\geq 0.75 \times 10^9/L$  and there is no other toxicity that precludes dosing of the patient. Note that once a dose has been restarted, subsequent declines in platelet or ANC count will require that [Table 5-4](#) be used to determine the new lower dose or dose interruption. It is required that patients who have restarted dosing have more frequent hematology assessments. PLT and ANC counts must be obtained at least weekly for 4 weeks, and then at least every second week for the next 4 weeks. Thereafter, they may resume monthly evaluations (exception: for grade 4 thrombocytopenia or neutropenia events please refer to [Section 5.1.2.9.1](#)).

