$\geq 75 \times 10^9 / L$ $50 - 74 \times 10^9 / L$ $35 - 49 \times 10^9 / L$ $25 - 34 \times 10^9 / L$ $< 25 \times 10^9 / L$	Continue at same dose level Continue at same dose level Continue at same dose level Continue at same dose level * Hold dosing  * qualifies as a DLT. If resolved to ≤ grade 2, resume therapy according to the rules of Table 5-6 .	Dose at the Time of the Platelet Decline 
 
 5 mg qd	5 mg b.i.d.	5 mg q.AM / 10 mg q.PM	10 mg b.i.d.	10 mg q.AM / 15 mg q.PM	15 mg b.i.d.	
 
 New Maximum Dose That Must be Instituted 
 
 Continue at same dose level	10 mg b.i.d.†	10mg b.i.d.†	
 
 Continue at same dose level	Continue at same dose level‡	
 
 Continue at same dose	5 mg b.i.d.	5 mg b.i.d.	5 mg b.i.d.	5 mg b.i.d.	
 
 5 mg qd	
 
 Discontinue	Hold dosing	
 
 †Patients from stratum 1 ‡Patients from stratum 2						5 mg qd	5 mg b.i.d.	5 mg q.AM / 10 mg q.PM	10 mg b.i.d.	10 mg q.AM / 15 mg q.PM	15 mg b.i.d.	Continue at same dose level			10 mg b.i.d.†	10mg b.i.d.†	Continue at same dose level			Continue at same dose level‡			Continue at same dose		5 mg b.i.d.	5 mg b.i.d.	5 mg b.i.d.	5 mg b.i.d.	5 mg qd	Discontinue	Hold dosing									
5 mg qd	5 mg b.i.d.	5 mg q.AM / 10 mg q.PM	10 mg b.i.d.	10 mg q.AM / 15 mg q.PM	15 mg b.i.d.																																					
Continue at same dose level			10 mg b.i.d.†	10mg b.i.d.†																																						
Continue at same dose level			Continue at same dose level‡																																							
Continue at same dose		5 mg b.i.d.	5 mg b.i.d.	5 mg b.i.d.	5 mg b.i.d.																																					
5 mg qd	5 mg qd	5 mg qd	5 mg qd	5 mg qd	5 mg qd																																					
Discontinue	Hold dosing																																									
In cases of grade 4 thrombocytopenia, follow-up rules according to Section 5.1.2.9.1 . For dose escalation or dose restart guidelines, see Table 5-5 and Table 5-6 .																																										

**Table 5-5 Dose escalation guidelines and allowed maximum doses for patients who have previously decreased dosing for thrombocytopenia**

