Current Platelet Count	Dose re-escalation guidelines (NOTE: maximum doses are given, lower doses may be used at Investigator's discretion)
25 x10  /L - 34 x10  /L	Continue at 5 mg qd until platelet counts $\geq$ 35 x10  /L
35 x10  /L - 49 x10  /L	Continue at 5 mg b.i.d. until platelet counts $\geq$ 50 x10  /L
$\geq$ 50 x10  /L	May increase dose by 5 mg qd each cycle (28 days) provided platelet count remains $\geq$ 50 x10  /L, up to the dose where platelet counts first declined and dose reduction occurred

**Table 5-6 Dose restart guidelines and allowed maximum doses for patients who have previously interrupted dose for grade 4 thrombocytopenia or grade 4 neutropenia**

Current platelet count	Dose restart guidelines (NOTE: maximum doses are given, lower doses may be used at investigator's discretion)
<35 x10  /L in a patient who is currently holding dose	Must continue to hold
35 - 49 x10  /L in a patient who is recovering from a dose hold	5 mg qd for 2 weeks, then increase in 5 mg qd increments, no faster than once every cycle (28 days), provided platelet counts $\geq$ 50 x10  /L
$\geq$ 50 x10  /L in a patient who is recovering from a dose hold	5 mg b.i.d. for at least 2 weeks, then may proceed with 5 mg qd dose increases, no more frequently than once every cycle (28 days), and provided platelets remain $\geq$ 50 x10  /L, up to the dose where platelet counts first declined < 25 x10  /L
Current ANC count	Dose restart guidelines (NOTE: maximum doses are given, lower doses may be used at investigator's discretion)
<0.75 x10  /L in a patient who is currently holding dose	Must continue to hold
0.75 – 1.00 x10  /L in a patient who is recovering from a dose hold	5 mg qd for 2 weeks, then increase in 5 mg qd increments, no faster than once every cycle (28 days), provided ANC counts $>$ 1.00 x10  /L
$>$ 1.00 x10  /L in a patient who is recovering from a dose hold	5 mg b.i.d. for at least 2 weeks, then may proceed with 5 mg qd dose increases, no more frequently than once every cycle (28 days), and provided ANC remain $>$ 1.00 x10  /L, up to a maximum dose of 5 mg qd BELOW the dose where ANC counts first declined < 0.50 x10  /L

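### After a platelet DLT in Days 1–28, Table 5-4 ties restart to grade 2 or better, while Section 5.1.4 and Table 5-6 allow it from 35 × 10⁹/L, so counts of 35–49 fall under two rules

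*Protocol*

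**What the plan says.** Platelet counts below are in units of 10⁹/L.

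- **Section 5.1.2.8** interrupts INC424 after a DLT and sends the patient to Table 5-4. Therapy may resume after recovery if the investigator thinks it in the patient's interest, but only after consultation with the Sponsors, and then under Section 5.1.3 and Table 5-4.
- **Table 5-4**, thrombocytopenia block, treatment-related toxicity in Days 1–28: a count below 25 means hold and is a DLT. The note continues "If resolved to ≤ grade 2, resume therapy according to the rules of" Table 5-6.
- **Section 5.1.4**: "Doses may be restarted and subsequently increased, according to the" Table 5-6, once platelets are back to at least 35, ANC to at least 0.75, and no other toxicity stands in the way.
- **Table 5-6** is headed "Dose restart guidelines and allowed maximum doses for patients who have previously interrupted dose for grade 4 thrombocytopenia or grade 4 neutropenia". It keeps the hold below 35. For a patient at 35–49 coming off a hold it gives "5 mg qd for 2 weeks, then increase in 5 mg qd increments, no faster than once every cycle (28 days), provided platelet counts" are at least 50. A separate row covers 50 and above.
- **Section 5.1.3** says that after a DLT the patient can resume at a reduced dose under Section 5.1.2.7, the section on intra-patient escalation.
- **Grades.** Section 5.1.4 states "Grading of toxicity will be according to CTCAE Version 4.03", without cut-points for platelets. Section 3.4.5 describes an analysis of earlier-study patients who "had extended (many weeks) periods of grade 1 or 2 platelet decline was carried out", made to find doses that went with stable counts of 50 to 100.
- **Interruption limit.** Sections 5.1.4 and 6.1.4 both require discontinuation when an interruption exceeds 28 days.

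**The concern.** Table 5-4 sets a condition by grade and then hands over to a table that sets its own condition by count. If grade 2 or better means about 50 and above, the two conditions differ, and the 35–49 row of Table 5-6 could not set the restart for the patients whom Table 5-4 has just sent there.

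Thrombocytopenia is the known DLT of this drug (Sections 1.2.4 and 1.3), and restart after a DLT is an expected path: Section 5.1.2.8 provides for it, and SAP Section 2.1.1 reworded the dose-determining set because of it. Two patients with the same count could therefore be handled differently, with different time off drug and possibly a different outcome under the 28-day limit.

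**Working it through.** No sample size, power or error rate is involved, and the plan gives no figure to reproduce. The check sets the passages side by side.

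**Step 1: put the grade condition into counts.** Let L be the lowest count that is still grade 2. The protocol does not print L. Section 3.4.5 associates grade 1 or 2 decline with 50 to 100, which implies L of about 50. Table 5-4 and Table 5-6 attach grade 4 to counts below 25, so grade 3 would run from 25 to 49. That is consistent with L = 50.

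**Step 2: compare the rules for a patient on hold after a platelet DLT** (ANC and other toxicity assumed not to prevent dosing).

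| Count | Table 5-4 note | Section 5.1.4 | Table 5-6 |
|---|---|---|---|
| below 35 | hold | hold | hold |
| 35–49 | condition not met | restart allowed | restart row given |
| 50 and above | restart | restart allowed | restart row given |

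The rules disagree in the middle row only. The two thresholds are 50 − 35 = 15 apart.

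**Step 3: vary L.** The conflict band is every count from 35 up to, but not including, L. With L = 50 it is 35–49. It disappears only if L is 35 or lower, which does not fit Section 3.4.5.

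**Step 4: look for an exemption.** The title of Table 5-6 covers every interruption for grade 4 thrombocytopenia, and Section 5.1.4 does not separate DLTs from later events. The grade condition stands only in the note attached to the Days 1–28 DLT. For grade 4 neutropenia, also a DLT when treatment-related in that window, Table 5-4 refers to Table 5-6 and adds no grade condition. Section 5.1.3 does not settle the matter, because Section 5.1.2.7 governs dose increases and states no count at which a held patient may restart.

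**Step 5: consequences.** Let t35 and t50 be the days from the start of the hold to a count of 35 and of 50.

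- Extra time on hold under the Table 5-4 note is t50 − t35.
- If t35 ≤ 28 < t50, the reading decides whether the patient must be discontinued.
- If the restart would fall inside the first cycle, relative dose intensity for that cycle (SAP Sections 2.2.2 and 2.2.5) also changes.

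The documents give neither t35 nor t50, so none of these can be sized. The effect may be sharpest in Stratum 2, whose qualifying range is 50–74: under the grade condition such a patient has to regain the bottom of the enrolment range first.

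**Step 6: what does not change.** The DLT is recorded before any restart, and SAP Section 2.1.1 keeps every patient with a DLT in the dose-determining set whether or not treatment resumes.

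**The case against.** The strongest reply is that Table 5-4 states a deliberately stricter rule for DLTs, and that Table 5-6 serves a wider group, including later and unrelated grade 4 events, so its 35–49 row still has users. Section 5.1.4 is permissive and Table 5-6 calls its contents guidelines, so a site that waits for grade 2 breaches neither. That is a coherent design, but no passage states it. Compliance also runs one way only: restarting at 35–49 satisfies Section 5.1.4 and Table 5-6 and fails Table 5-4.

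Three stronger readings are tempting and are not supported.

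- **That the site alone decides by whichever table it reads.** Section 5.1.2.8 requires consultation with the Sponsors before any DLT patient resumes. This is a real safeguard, though it gives the Sponsors no single written threshold to apply.
- **That every recovering patient is caught.** The first band above 25 is 25–34, where all the passages hold dosing. Section 5.1.2.9.1 recommends weekday counts only until grade 3 or better, and Section 6.1.4 then requires at least weekly follow-up, so a count can pass from below 35 to 50 or more between draws.
- **That the protocol defines grade 2 as 50 and above.** Section 3.4.5 describes a retrospective analysis. It implies the cut-off and does not define it.

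Table 5-4 is also damaged by text extraction. The note is nevertheless tied to the DLT flag, which belongs to treatment-related events in Days 1–28.

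**Conclusion.** The inconsistency is real and narrow. For treatment-related platelet DLTs in Days 1–28, counts of 35–49 meet the restart condition of Section 5.1.4 and Table 5-6 and do not meet that of Table 5-4.

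This rests on two assumptions: that grade 2 ends at about 50, as Section 3.4.5 implies, and that the Table 5-4 note is a condition for restart, which is its natural sense.

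It bears on patient safety, exposure and the 28-day limit, to an extent that the documents do not allow to be quantified. A reader might infer that the dose-finding result is affected. It is not: the DLT count, the logistic model and the MSSD estimate are the same under either threshold. The documents do not show which threshold is intended, and this review takes no position on it.

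**What to change.** Reconcile the Table 5-4 note, Section 5.1.3, Section 5.1.4 and Table 5-6 in one of two ways. Either state one restart condition for these patients in platelet units, chosen by the clinical team, or state explicitly that patients with a Days 1–28 platelet DLT follow a different condition from other grade 4 interruptions, and give it in platelet units. In the same edit, settle whether the pointer from Section 5.1.3 to Section 5.1.2.7 is meant to govern restart. The cost is amendment wording.

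Optionally, add to the CSR a listing of restarts after a platelet DLT with the count at restart and the days on hold. SAP Sections 2.2.2, 2.3.2 and 2.3.3 already list dosing, DLTs and laboratory values, so this joins planned data and needs no new collection. If recruitment has closed by the September 2017 date in Section 3.1, this listing is the part that remains useful.

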#### **5.1.2.5 Safety expansion phase**

Once the MSSD of INC424 is identified for both strata in the dose escalation phase of this study, additional patients will be enrolled and treated at this dose in order to further evaluate its safety and tolerability and to obtain estimates of efficacy, with the purpose of establishing that this dose is suitable for use in the low-platelet population of patients with MF. Patients from both strata can be enrolled simultaneously during the safety expansion phase. If the MSSD is identical in both strata, all patients in the safety expansion phase will be treated with the same dose. Prior to Amendment 4, twenty patients (10 patients from each stratum), in addition to the patients treated at the MSSD during the dose escalation phase, were to be evaluated during this part of the study. If the MSSD proves not to be well tolerated with further experience and via continuous update of the Bayesian logistic regression model during this safety expansion phase, then a lower dose may be evaluated to twenty additional patients (10 patients from each stratum).

With the approval of Amendment 4, all new patients enrolled to Stratum 1's safety expansion phase will be given the 10 mg BID dose, instead of the 15 mg BID dose level previously evaluated as the MSSD. This will allow 10 mg BID to be evaluated as the starting dose. Approximately 20 patients will be evaluated at this dose level in Stratum 1, inclusive of the patients already enrolled into this dose during the dose escalation phase, OR the Last Patient's First Visit (LPFV) will occur on 01 September 2017, whichever comes first. Patients already taking the 15 mg BID dose in Stratum 1's safety expansion phase will continue to take their assigned dose. Stratum 2 will maintain its original enrollment requirement of 10 patients at the MSSD.

The criteria for continuation of treatment and dose modification guidelines employed during the dose escalation phase will also be followed during safety expansion phase. Dose escalation above the MSSD will not be allowed.

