NOTE: Whether the dose interruption occurred because of neutropenia, thrombocytopenia or both, when restarting, both the platelet count and ANC must be considered to determine the restart dose, with the lower calculated dose being used. Also, the maximum dose should always be 5 mg qd **BELOW** the dose where platelet counts first declined < 25 x10^9/L or ANC counts first declined < 0.5 x10^9/L.

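### Table 5-6 and the NOTE beneath it set maximum doses 5 mg/day apart after a hold for platelets below 25 ×10⁹/L; the operative text leans to the lower one, but no text expressly ranks them

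*Protocol*

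**What the plan says.** Protocol Section 5.1.4 sends restarts after a hold to Table 5-6.

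- **Row for platelets of at least 50.** The restart is "5 mg b.i.d. for at least 2 weeks, then may proceed with 5 mg qd dose increases", at most once per 28-day cycle while platelets stay at or above 50, "up to the dose where platelet counts first declined < 25" ×10⁹/L.
- **Row for ANC above 1.00.** The restart dose is the same, but the limit is "up to a maximum dose of 5 mg qd" *below* the dose at which ANC first fell under 0.50.
- **NOTE under the table.** It applies whether the hold was for neutropenia, thrombocytopenia or both. It says "both the platelet count and ANC must be considered to determine the restart dose, with the lower calculated dose being used". It then adds "Also, the maximum dose should always be 5 mg qd" *below* the dose at which platelets first fell under 25 or ANC first fell under 0.5.
- **Dose column headers of Tables 5-5 and 5-6.** Both say "maximum doses are given, lower doses may be used at Investigator's discretion".

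**The concern.** The row and the NOTE each state a maximum for the same patient and the same trigger, and the maxima differ. A site that follows the row to its limit breaks the NOTE. The ANC row agrees with the NOTE, so the platelet row is the odd one out.

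The practical question is whether a patient may go back to the dose at which platelets fell below 25. Thrombocytopenia is the dose-limiting toxicity of this drug (Section 1.2.4), and everyone here is meant to enter with platelets between 50 and 99, so this is a central safety rule.

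The answer also decides whether dosing at the row's limit is a protocol deviation. Section 11 does not permit authorized deviations, and Protocol Section 9.3 and SAP Section 2.2.5 list and summarize deviations.

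**Working it through.** The plan gives no figure to reproduce. The check compares the two caps at each dose level and then looks for text that ranks them.

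**Inputs.** The total daily doses in Table 5-2 are 10, 15, 20, 25 and 30 mg. A step of 5 mg qd is 5 mg/day. Let D be the daily dose at which platelets first fell below 25.

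**Caps.** Row cap = D. NOTE cap = D − 5. Gap = 5 mg/day, or 5/D as a share of the row cap.

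| First decline on | Row cap (mg/day) | NOTE cap (mg/day) | Gap as share of row cap |
|---|---|---|---|
| 5 mg b.i.d. | 10 | 5 | 5/10 = 50% |
| 5 mg AM / 10 mg PM | 15 | 10 | 5/15 = 33.3% |
| 10 mg b.i.d. | 20 | 15 | 5/20 = 25% |
| 10 mg AM / 15 mg PM | 25 | 20 | 5/25 = 20% |
| 15 mg b.i.d. | 30 | 25 | 5/30 = 16.7% |

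In stratum 2 only the first three lines apply, because SAP Section 2.1.1 gives 10 mg b.i.d. as the highest level reached there.

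**Restart dose against the NOTE cap.** The row restarts at 2 × 5 = 10 mg/day.
- D = 10: the cap is 10 − 5 = 5, so the restart dose is above the cap at once.
- D = 15: the cap is 10, equal to the restart dose.
- D of 20 or more: the cap is at least 15, so the conflict arises only on later increases.

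The row for ANC above 1.00 has the same defect within a single row. If ANC first fell under 0.50 on 5 mg b.i.d., its cap is 10 − 5 = 5 mg/day and its restart dose is 10 mg/day.

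**Does other text rank the two caps?**
- The lower-dose rule in the NOTE chooses between the platelet-based and ANC-based restart doses. It does not compare the row cap with the NOTE cap.
- The general ceilings do not bite. Section 5.1.2.7 limits doses to 15 mg b.i.d. in the first 24 weeks, then to the higher of the stratum MSSD and 10 mg b.i.d.; Section 5.1.2.5 adds "Dose escalation above the MSSD will not be allowed" for the expansion phase. With an MSSD of 15 mg b.i.d. in stratum 1 and 10 mg b.i.d. in stratum 2, the MSSD ceilings are 30 and 20 mg/day, at or above the row cap.
- The Section 5.1.2.7 sentence on treatment-related toxicity of grade 3 or worse mentions grade 4 thrombocytopenia separately. If those words belonged to the exemption for thrombocytopenia they would be redundant. The natural reading bars a second escalation to the level where grade 4 thrombocytopenia occurred, which fits the NOTE.
- Section 5.1.3 has patients resume at a reduced dose after a DLT. This also fits the NOTE, though it speaks of resumption and not of the later ceiling.
- The Amendment 3 rationale describes allowing a restart up to the dose of first decline, which fits the row. It is evidence of intent, not an operative rule.

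**The case against.** The strongest reply is that the protocol already answers the question. The NOTE says *always*, sits directly under the table and covers thrombocytopenia holds. The table gives maxima and allows lower doses, so a site that uses the lower cap breaches neither rule. Sections 5.1.2.7 and 5.1.3 lean the same way.

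Safeguards also exist. The Sponsors must be consulted before therapy resumes after a DLT (Section 5.1.2.8) and before any intra-patient escalation (Section 5.1.2.7). Platelets are checked at least weekly for 4 weeks after a restart and at least every second week for the next 4 (Section 5.1.4). The row itself requires platelets to stay at or above 50.

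Most of this stands, and it limits the severity. It does not remove the contradiction. If the NOTE always overrides, the row's cap can never operate, yet the Amendment 3 rationale presents that cap as a deliberate change. The consultation rules name no cap.

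A reader might infer that the text is evenly balanced. It is not: the only support for the row outside the table is the non-operative rationale. A reader might also try to date when the caps diverge for each dose level. The documents do not support such dates, because they do not say whether the Section 5.1.2.7 conditions govern Table 5-6 restarts. Those conditions include escalation only once every two cycles and platelet minima that, if they apply, would ordinarily block escalation in the first 24 weeks after a fall below 25. Nor are the five dose levels equally exposed. From Day 29, Table 5-4 steps the dose down as platelets fall below 50 and again below 35, and Amendment 4 starts new stratum 1 expansion patients at 10 mg b.i.d.

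**Conclusion.** The point holds. Current operative text states two maxima 5 mg/day apart for the same situation, a gap of 17% to 50% of the dose at first decline. For a first decline on 5 mg b.i.d., the row's restart dose breaks the NOTE immediately. The operative text favours the NOTE, but no sentence expressly ranks the two. It should be fixed because it is a conflicting safety instruction, and the correction is small.

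A reader might infer that the MSSD finding is affected. The documents do not support that. Platelets below 25 count as a DLT only if treatment-related and by Day 28 (Section 5.1.2.8), and the conflict concerns dosing after that event. There is no direct effect on the cycle 1 DLT count, the Bayesian logistic regression model or the sample size. The documents do not say how many patients are affected.

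The conclusion assumes that the NOTE applies to a hold for platelets alone, as its opening words state. A first fall below 25 on 5 mg qd is outside the point, because that requires discontinuation (Table 5-4, Section 6.1.4).

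**What to change.** 1. Reword the limit in the Table 5-6 row for platelets of at least 50 on the pattern of the ANC row: "up to a maximum dose of 5 mg qd" *below* the dose at which platelets first fell under 25 ×10⁹/L. The row, the NOTE and the ANC row then agree.
2. State that a patient whose first decline (platelets below 25 or ANC below 0.5) was on 5 mg b.i.d. restarts at 5 mg qd and does not exceed it.
3. Tell sites now to use the lower cap until the text is corrected.

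If the sponsor instead intends the Amendment 3 wording, it must remove the platelet clause from the NOTE so that one cap remains. The Section 5.1.2.7 sentence on grade 4 thrombocytopenia would then need to agree. The 35–49 row, which has no limit of its own tied to the dose of first decline, would need one. The ANC restart dose needs item 2 in either case.

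The cost is a protocol clarification and a site letter, with no new data and no SAP change. The downside of the main fix is that some patients lose the option of returning to their earlier dose.
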